### 7.2 Secondary Outcome Variables

Feasibility:

- Technical success of the cTACE procedure (technical failure is defined as the inability to administer the cTACE material, in which case the patient would be excluded from the study)
- Dose of doxorubicin delivered

Safety:

- All toxicities assessed as being at least possibly related, up to the 3-4 week follow-up visit (post cTACE) will be collected. Toxicities will be analyzed by descriptive statistics to show type, grade (NCI Common Toxicity Criteria v4.0), frequency and time from cTACE.

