## 5. Study Design/Investigational Plan

### 5.1 Overall Design

The study is a single site, prospective study, designed to measure the PK of doxorubicin and its metabolite doxorubicinol at various timed intervals after cTACE in patients with primary or metastatic liver cancer.

Up to 30 patients will be enrolled that meet study entry criteria; approximately 15 with primary liver cancer and 15 with secondary liver cancer. Up to 40 patients may be consented if necessary in order to enroll these 30 patients, to account for potential patients who screen-out or who are unable to complete sample collection for the PK (80% of planned draws). 15 patients will be enrolled into the lobar cTACE arm and 15 patients will be enrolled into the superselective cTACE arm. The assignment of the treatment arm will be determined by the PI or a designated radiologist after review of the patient's imaging and history.

The study is planned to complete enrollment in two years, with another month to conclude patient follow-up.

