## 6. Adverse Event Collection and Reporting Requirements

### 6.1 Definitions

An Adverse Event (AE) is defined as any new untoward medical occurrence or worsening of a pre-existing medical condition in a patient and that does not necessarily have a causal relationship with this treatment. An AE can therefore be any unfavorable and unintended sign (including abnormal laboratory finding, for example), symptom, or disease temporally associated with the treatment.

A Serious AE (SAE) is an untoward medical occurrence that at any dose produces any of the following outcomes:

- Results in death;
- Is life threatening (defined as an event in which the subject was at risk of death at the time of the event; it does not refer to an event which hypothetically might have caused death if it were more severe):

- Requires inpatient hospitalization or causes prolongation of existing hospitalization (see NOTE below for exceptions);
- Results in persistent or significant disability/incapacity;
- Is a congenital anomaly/birth defect;
- Is an important medical event (defined as a medical event(s) that may not be immediately life-threatening or result in death or hospitalization but, based upon appropriate medical and scientific judgment, may jeopardize the subject or may require intervention [e.g., medical, surgical] to prevent one of the other serious outcomes listed in the definition above). Examples of such events include, but are not limited to: intensive treatment in an emergency room or at home for allergic bronchospasm; blood dyscrasias or convulsions that do not result in hospitalization.

NOTE:

The following hospitalizations are not considered SAEs:

- Admissions as per protocol for a planned medical/surgical procedure;
- Routine health assessment requiring admission for baseline/trending of health status (e.g., routine colonoscopy);
- Medical/surgical admission for purpose other than remedying ill health state and was planned prior to entry into the study. Appropriate documentation is required in these cases;
- Admission encountered for another life circumstance that carries no bearing on health status and requires no medical/surgical intervention (e.g., lack of housing, economic inadequacy, care-giver respite, family circumstances, administrative).

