## 6.3 Adverse Event Capture and Reporting

Risks associated with the research procedures are expected to be minimal, and are involved with the drawing of blood and the placement of the IV catheter (second sheath). They include pain, bruising, swelling and bleeding when the catheter is placed. There is also a risk of infection at the IV site, and very rarely, nerve damage.

HIC #: 1506016008  
[name]

Adverse Events are collected through 3-4 weeks post cTACE and documented for each patient on the AE case report form (CRF). The AEs are transcribed onto a study-specific electronic AE log which is reviewed regularly by the PI and is available for the IRB and monitoring committees for review.

Study deviations (protocol deviations: PDs) are collected and reported in the same way as the AEs are managed. PDs are collected through 3-4 weeks post cTACE, and documented on CRFs and into PD electronic logs, which are reviewed regularly by the PI and available for IRB and monitoring committees for review.

Unanticipated Problems Involving Risks to Subjects and Others (UPIRSOs) that may require a temporary or permanent interruption of study activities will be reported immediately (if possible), followed by a written report within 5 calendar days of the Principal Investigator becoming aware of the event to the IRB (using the appropriate forms from the website) and any appropriate funding and regulatory agencies. The investigator will apprise fellow investigators and study personnel of all UPIRSOs and adverse events that occur during the conduct of this research project via email as they are reviewed by the PI. The Cancer Center Protocol Review Committee (PRC), Yale Cancer Center Data and Safety Monitoring Committee (DSMC), study sponsor, funding and regulatory agencies will be informed of serious adverse events within 5 days of the event becoming known to the Principal Investigator.

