### 7.3 Statistical Plan

Up to 40 patients may be consented in order to enroll 30 patients, and to account for patients who are unable to complete sample collection for the PK (80% of planned draws). 15 patients will be enrolled into the lobar cTACE arm and 15 patients will be enrolled into the superselective cTACE arm.

We have assumed a clinically significant change in doxorubicin exposure would be 50%. In order to have 80% power to detect a 50% change with a 5%  $\alpha$ , the sample size varies depending on the variability noted with TACE therapy. In the Varella trial utilizing cTACE with a Lipiodol doxorubicin formulation, the variability was reported as 30% Coefficient of Variation (CV). In our recent trial (J1306) utilizing TACE with a Drug Eluting Bead (DEB) doxorubicin formulation, the variability was reported as 90% CV. We anticipate the Lipiodol formulation to behave more like the Varella trial with 15 patients allowing for slightly higher variability.

*%CV	30%	43%	90%
Expected Sample Size	8	15	58

\*Methodology/calculator accessed from the websites below on 11/6/2014:

[https://www.statstodo.com/SSizBioequiv\\_Tab.php](https://www.statstodo.com/SSizBioequiv_Tab.php)

[https://www.statstodo.com/SSizBioequiv\\_Pgm.php#](https://www.statstodo.com/SSizBioequiv_Pgm.php#)

Continuous variables will be reported as means and standard deviations, medians and ranges, or both. Categorical variables will be reported as numbers and percentages. Pharmacokinetic parameters will be calculated by standard noncompartmental methods using Phoenix WinNonlin 6.1 (Pharsight, Mountain View, CA) for each patient. Pharmacokinetic parameters will be summarized using descriptive statistics.

Comparisons of the pharmacokinetic profiles between the lobar cTACE group and the superselective cTACE group will be performed using the Mann-Whitney U test. Correlations between pharmacokinetic profiles and clinical toxicities will be performed using the Kruskal-Wallis one-way ANOVA test. Correlations between the pharmacokinetic profiles and tumor burden will be performed with the Spearman's correlation coefficient. A P value < 0.05 will be considered statistically significant in all cases.

HIC #: 1506016008  
[name]

Interim analysis:

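### The safety analysis is limited to toxicities assessed as at least possibly related, although adverse events are captured regardless of cause, and the plan does not say who assesses relatedness or to what

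*Combined protocol and SAP*

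**What the plan says.** All references are to the combined protocol and SAP.

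- **Safety outcome (7.2, same wording in 2.2):** "All toxicities assessed as being at least possibly related, up to the 3-4 week follow-up visit (post cTACE) will be collected". The method follows: "Toxicities will be analyzed by descriptive statistics to show type, grade (NCI Common Toxicity Criteria v4.0), frequency and time from cTACE". The synopsis applies the same relatedness filter, but to what is analysed rather than to what is collected.
- **Definition (6.1):** an adverse event is one "that does not necessarily have a causal relationship with this treatment".
- **Capture (6.3):** "Adverse Events are collected through 3-4 weeks post cTACE and documented for each patient on the AE case report form". No relatedness condition is attached.
- **PK and toxicity (7.3):** "Correlations between pharmacokinetic profiles and clinical toxicities will be performed using the Kruskal-Wallis one-way ANOVA test". Sections 2.1 and 7.1 list toxicity as a correlate of the PK profile under the primary outcome. None of these sections defines the toxicity variable.
- **Arm (5.1):** "The assignment of the treatment arm will be determined by the PI or a designated radiologist". No masking is described anywhere.
- **Oversight (6.3, 8.1):** the PI reviews the adverse event log and conducts the safety reviews. Section 8.1 uses graded relatedness categories to define reportable events, but names no assessor and does not say what an event must be related to.

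**The concern.** The set of events to be analysed is narrower than the set recorded, and a causality assessment that the plan does not describe makes the difference. Events assessed as unrelated appear in no planned summary.

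Causality is hard to assess here. Each patient receives doxorubicin, mitomycin-C, Lipiodol and embolic particles in one procedure (5.1.1), on top of active liver cancer and often impaired liver function. There is no untreated comparison group. Section 1.5 states an expectation that the superselective approach has fewer adverse events and lower serum doxorubicin. The treating team knows the approach and the amount delivered. Where masking is absent and criteria are unwritten, such expectations can influence which events are called related.

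At stake are the whole of the safety outcome and, if the same filter is carried into 7.3, the toxicity side of the PK correlation. The primary PK parameters themselves are laboratory measurements and are not touched.

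**Working it through.** The plan attaches no figure to this point. Its one calculation, the sample-size table in 7.3, concerns doxorubicin exposure and does not enter here. The check is a comparison of sections, plus simple arithmetic on rates in section 1.6.

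**Step 1. Recorded set against analysed set.**

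| | Recorded | Analysed for safety |
|---|---|---|
| Source | 6.1, 6.3 | Synopsis, 2.2, 7.2 |
| Causality needed? | No | Yes, at least possibly related |
| Window | To 3-4 weeks after cTACE | Same |

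The windows agree and the causality condition does not. In addition, 2.2 and 7.2 apply the condition to collection, which conflicts with 6.3.

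**Step 2. What an event must be related to.** The text leaves three readings open. With N = 30, expected patients = rate × 30.

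1. *cTACE as a whole.* Section 1.6 gives post-embolization syndrome in 60% to 80% of patients: 0.60 × 30 = 18 and 0.80 × 30 = 24.
2. *Doxorubicin.* Section 1.6 says the syndrome occurs whether or not a chemotherapy drug is used, so a strict assessor could leave it out. One drug-type effect with a stated rate is bone marrow toxicity, at under 4%: 0.04 × 30 = 1.2, so about one patient. Other drug effects would add to this; the section gives no usable rate for them.
3. *The research procedures.* Section 6.3 describes the research risks as those of blood sampling and the IV catheter, and 5.1.1 treats cTACE as routine care. Almost no cTACE toxicity would count. No rate is given.

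The same 30 patients could thus yield a safety table covering most of them or very few. These counts are illustrations from background rates. They show how much depends on an unstated definition and do not predict the result.

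**Step 3. When the filter biases a comparison.** Let p be the true event rate, equal in two groups, and q1 and q0 the probabilities that an event is called related in each group. The apparent difference is p × (q1 − q0). If q1 = q0 it is zero: with p = 0.60 and q = 0.90 in both groups, each shows 0.54. The filter creates a spurious difference only when attribution differs between groups. The documents give neither q1 nor q0, so no size can be derived.

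**Step 4. Where the filter could enter.** The safety summary is descriptive and not specified by arm. The planned arm comparison is of PK profiles (7.3, Mann-Whitney). The PK-toxicity test uses a toxicity variable that is undefined. The filter is therefore certain in the safety summary, possible in the PK-toxicity test and absent from the arm comparison.

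**The case against.** The case on the other side is substantial.

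- **The filter may remove little.** Timing in 7.2 is counted from cTACE, so relatedness to cTACE as a whole is the most natural reading. At least possibly related is a low threshold and does not require separating drug from embolization. Section 1.6 attributes post-embolization syndrome to embolization itself, so nearly all such events should pass in both arms. This stands, and it is why no magnitude is claimed.
- **A reader might infer a biased comparison of toxicity between arms.** The documents plan no such comparison. An unplanned one would also be confounded by the choice of arm from imaging and history, whichever events were counted.
- **A reader might infer that the PK-toxicity test is restricted to related events.** Section 7.3 does not say so. That reading rests on 2.2 and 7.2 being the only places where toxicities are specified. What the text establishes is an undefined variable.
- **A reader might infer that unblinded investigators who know the PK results make the attribution.** No section names the assessor; the documents merely describe no masking. Samples are frozen and batched to an outside laboratory, with shipment allowed up to 3 months after the last sample (5.1.2), while adverse event collection ends at 3-4 weeks. A patient's own Cmax and AUC would usually be unknown at the time. The interim review follows completion by the 16th patient, so it could inform attribution in at most the later 30 − 16 = 14. Knowledge of approach and dose remains a possible route.
- **Related-only reporting is defensible** in a small, largely descriptive study, and all-cause events add disease-related noise. This is a reason to keep the related subset as a second display. It does not justify having no all-cause summary.

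**Conclusion.** The point holds as a cheap improvement. It is established that the safety outcome covers only events assessed as at least possibly related, that 6.1 and 6.3 define and capture events regardless of cause, that no all-cause summary is planned, and that the assessor, the meaning of related and any masking are unspecified. It is also established that the collection wording in 2.2 and 7.2 conflicts with 6.3 and that the toxicity variable in 7.3 is undefined.

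Attribution bias is a risk and is not shown to occur. Its size is not estimable from the documents: it would be zero with equal attribution, and any other figure would need attribution rates that the plan does not give. The planned PK comparison of lobar and superselective cTACE is unaffected. The conclusion assumes that 6.3, rather than the collection wording in 2.2 and 7.2, governs what goes on the case report form.

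**What to change.** 1. In 2.2 and 7.2, and in the synopsis to match, summarise all adverse events from cTACE to the 3-4 week visit by type, grade, frequency and time, regardless of attribution. Show the at least possibly related subset second.
2. State who assesses relatedness, to what and by which criteria, and whether that person is masked to arm and dose.
3. In 7.3, define the toxicity variable for the Kruskal-Wallis analysis as each patient's maximum CTCAE grade over all adverse events, with a related-only sensitivity analysis.
4. Reconcile the collection wording in 2.2 and 7.2 with 6.3.

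Scheduled laboratory values are not a good substitute for the toxicity variable. The Study Visit Calendar has chemistry and hematology only at screening and Day 21-28, whereas section 1.6 puts the aminotransferase peak at 3-5 days, with return to baseline by 10-14 days.

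Cost: one more table, one sensitivity analysis and a few sentences, using data that 6.3 already places on the case report form. If 7.2 has been followed literally, unrelated events would also have to be recorded from now on. Downside: more background, disease-related events in the tables and some added noise in the PK correlation.

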### 7.3 Statistical Plan

Up to 40 patients may be consented in order to enroll 30 patients, and to account for patients who are unable to complete sample collection for the PK (80% of planned draws). 15 patients will be enrolled into the lobar cTACE arm and 15 patients will be enrolled into the superselective cTACE arm.

We have assumed a clinically significant change in doxorubicin exposure would be 50%. In order to have 80% power to detect a 50% change with a 5%  $\alpha$ , the sample size varies depending on the variability noted with TACE therapy. In the Varella trial utilizing cTACE with a Lipiodol doxorubicin formulation, the variability was reported as 30% Coefficient of Variation (CV). In our recent trial (J1306) utilizing TACE with a Drug Eluting Bead (DEB) doxorubicin formulation, the variability was reported as 90% CV. We anticipate the Lipiodol formulation to behave more like the Varella trial with 15 patients allowing for slightly higher variability.

*%CV	30%	43%	90%
Expected Sample Size	8	15	58

\*Methodology/calculator accessed from the websites below on 11/6/2014:

[https://www.statstodo.com/SSizBioequiv\\_Tab.php](https://www.statstodo.com/SSizBioequiv_Tab.php)

[https://www.statstodo.com/SSizBioequiv\\_Pgm.php#](https://www.statstodo.com/SSizBioequiv_Pgm.php#)

Continuous variables will be reported as means and standard deviations, medians and ranges, or both. Categorical variables will be reported as numbers and percentages. Pharmacokinetic parameters will be calculated by standard noncompartmental methods using Phoenix WinNonlin 6.1 (Pharsight, Mountain View, CA) for each patient. Pharmacokinetic parameters will be summarized using descriptive statistics.

Comparisons of the pharmacokinetic profiles between the lobar cTACE group and the superselective cTACE group will be performed using the Mann-Whitney U test. Correlations between pharmacokinetic profiles and clinical toxicities will be performed using the Kruskal-Wallis one-way ANOVA test. Correlations between the pharmacokinetic profiles and tumor burden will be performed with the Spearman's correlation coefficient. A P value < 0.05 will be considered statistically significant in all cases.

HIC #: 1506016008  
[name]

Interim analysis:

After the 16th patient has completed the study, including approximately 8 in each cTACE arm, the PK parameters will be measured for each patient in order to formally review the accumulated data and to inform the investigators whether any protocol modifications need to be made.

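### The study is sized on a 50% change in exposure, but no between-arm effect estimate or confidence interval is planned, only a Mann-Whitney P value

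*Combined protocol and SAP*

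**What the plan says.** Section 7.3 (Statistical Plan) sets the effect of interest in relative terms: "We have assumed a clinically significant change in doxorubicin exposure would be 50" percent. It asks for 80% power at a 5% alpha and takes variability from two earlier trials. A cTACE trial with a Lipiodol formulation gave a CV of 30%. For the team's own drug-eluting bead trial, "the variability was reported as 90% CV". The row "Expected Sample Size" shows 8, 15 and 58 for CVs of 30%, 43% and 90%. The plan expects the Lipiodol formulation to resemble the first trial, "with 15 patients allowing for slightly higher variability".

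The lobar versus superselective comparison is listed under the primary outcome (Sections 2.1 and 7.1). For its analysis, Section 7.3 says only that it "will be performed using the Mann-Whitney U test", with P < 0.05 as the criterion in all cases. On summaries it says "Continuous variables will be reported as means and standard deviations, medians and ranges, or both". A separate sentence says that PK parameters get descriptive statistics, without naming them.

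The documents nowhere specify a ratio or percent difference between arms, a log transformation, a geometric mean, a Hodges-Lehmann estimate or a confidence interval. The only interval in the text belongs to a cited survival trial in Section 1.4.

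**The concern.** The sample size rests on how large the change in exposure is, while the planned comparison reports only whether the two distributions differ detectably. A significant result could come from a change well under 50%. A non-significant one could come from similar exposure or from high variability. The Synopsis says it matters whether superselective delivery lowers serum exposure and that the findings could alter practice. A reader would want to know how much lower exposure is and how precisely that is known, and no planned output gives this.

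**Working it through.** **Inputs, all from Section 7.3:** 50% change; 80% power; 5% alpha (sidedness not stated, taken as two-sided below except where noted); CV 30%, 43% and 90%; 15 patients per arm.

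**Step 1. The plan's own sample sizes.** The closest match is an equivalence calculation (two one-sided tests) with a margin of 50% of the mean and no true difference:

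n per arm = 2 × [CV × (t(0.95) + t(0.90)) / 0.5]², iterated on 2n − 2 degrees of freedom.

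This gives 8, 14 and 57, against 8, 15 and 58 stated. A two-sided normal calculation for a log ratio of 1.5 gives 9, 17 and 57, nearly as close. A log ratio of 0.5 gives 3, 6 and 20, which does not fit. The stated figures are therefore reproduced within 1 or 2 patients, but they do not reveal which scale or direction of change was meant.

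**Step 2. Precision of a between-arm ratio with 15 per arm.** Assume lognormal data with the same CV in both arms.

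- Log-scale SD: s = √ln(1 + CV²)
- Half-width on the log scale: h = t(0.975, 28) × s × √(2/15) = 2.048 × s × 0.365
- The 95% interval is the observed ratio divided and multiplied by exp(h)

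| CV | s | h | exp(h) | Observed ratio at P = 0.05 | Observed reduction |
|---|---|---|---|---|---|
| 30% | 0.294 | 0.220 | 1.25 | 0.80 | about 20% |
| 43% | 0.412 | 0.308 | 1.36 | 0.73 | about 27% |
| 90% | 0.770 | 0.576 | 1.78 | 0.56 | about 44% |

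The last two columns use exp(−h), the point at which a log-scale t-test reaches P = 0.05. This stands in for the Mann-Whitney test, which has no exact threshold expressed as a ratio.

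**Step 3. A significant result need not mean a 50% change.** In simulated Mann-Whitney tests on lognormal data with 15 per arm:

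- at CV 30%, a true 25% reduction gives P < 0.05 in about 70% of trials;
- at CV 43%, a true 30% reduction does so in about 59%.

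For example, an observed ratio of 0.70 at CV 30% has an interval of 0.70/1.246 to 0.70 × 1.246, that is 0.56 to 0.87. The result is significant, yet it excludes a halving. The planned output would report only the first of these facts.

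**Step 4. A non-significant result need not exclude a 50% change.** Simulated Mann-Whitney power with 15 per arm:

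| CV | True ratio 0.5 | True ratio 1.5 |
|---|---|---|
| 30% | about 100% | about 94% |
| 43% | about 99% | about 70% |
| 90% | about 61-64% | about 26% |

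At CV 90%, an observed ratio of 0.60 has an interval of 0.60/1.779 to 0.60 × 1.779, that is 0.34 to 1.07. It is not significant, and a halving is not excluded. At CV 43%, power differs by 29 percentage points between the two readings of a 50% change (99% − 70%), so the direction and reference arm need stating.

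**The case against.** Several counter-arguments have force.

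- **Geometric means are not ruled out.** PK parameters have their own sentence promising unspecified descriptive statistics, and the plan never calls its means arithmetic. A reader might infer that the study could never yield a ratio. That goes too far: a crude percent change can be read from the arm summaries, and an approximate interval can be worked out from means, SDs and numbers. What stands is that no estimate or interval is prespecified, and that the form of summary is left open.
- **The plan speaks of a change, not a ratio.** A reader might infer that the study was sized for a ratio. Step 1 does not establish that, since an additive margin fits best. A 50% change is still relative on either reading, and no relative estimate is planned.
- **The 90% CV is not what the plan expects.** It comes from a bead formulation. At 30% and 43%, power for a halving is about 100% and 99%, so a null result would be informative about a halving. A reader might also infer that means with SDs describe these data badly because mean − 1.96 SD is negative. That happens only at CV 90% (1 − 1.96 × 0.9 = −0.76 of the mean). At 30% and 43% it is 0.41 and 0.16. Step 4 is therefore a worst case for a halving, whereas Step 3 applies at the CVs the plan does expect.
- **The Synopsis labels the study Phase I and not hypothesis driven, and a rank test is a defensible choice.** Both are true. A study without a hypothesis has more reason to estimate, and an interval can accompany the rank test without displacing it.
- **The arms are not comparable by design.** The investigator or a designated radiologist chooses the arm from imaging and history (Section 5.1), and the amount given is titrated to the treated area (Section 5.1.1). An interval would cover sampling error only and could not attribute a difference to technique. This limits the P value equally, and the fix has to say so.

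**Conclusion.** The point holds as an omission in the analysis plan that should be corrected. The study is sized on a relative change of 50%, and its between-arm comparison has no prespecified effect estimate or interval. At the CVs the plan expects, significance can reflect an observed reduction of only about 20% to 27%. At CV 90%, which the plan does not expect, power for a true halving is about 61-64%, so a null result would leave one possible.

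These figures assume lognormal data, equal CVs in the two arms, 15 evaluable patients per arm and a two-sided 5% test. The documents give CVs but say nothing about the shape of the distribution. A reader might infer that the sample size is wrong. The documents do not support that, because 8, 15 and 58 are closely reproduced.

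**What to change.** In Section 7.3, for AUC and Cmax of both doxorubicin and doxorubicinol:

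- report the geometric mean and geometric CV by arm;
- report the superselective/lobar geometric mean ratio with a 95% confidence interval from log-transformed data, or a Hodges-Lehmann shift on the log scale with its interval, which pairs naturally with the Mann-Whitney test;
- read the interval against the 50% criterion, stating its direction and reference arm (half the lobar exposure is a ratio of 0.50, whereas lobar exposure 50% above superselective is 1/1.5 = 0.67);
- label the ratio an unadjusted descriptive contrast, because the arm is chosen by the investigator and the delivered dose is titrated.

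Keep the Mann-Whitney test, and use median and range for Tmax. The cost is a few sentences and a standard output table, with no new data or patients. The geometric mean ratio brings a lognormal assumption. The Hodges-Lehmann version needs only a common shape on the log scale.

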### 4.2 Registration Process

Patients consented for the study will be registered with OnCore, Yale's Clinical Trials Management System, and be assigned a study identifier and counted for the final data analysis. Patients' progress while on the study will be managed via OnCore.

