### 5.1.2 Research Procedures

Based on previous methodology utilized in our research trial J1306 at Johns Hopkins and other TACE trials, venous blood will be sampled for doxorubicin concentrations just before the cTACE (pre-) and then repeatedly after cTACE at the following time points: 5 minutes, 10 minutes, 20 minutes, 40 minutes, 1 hour, 2 hours, 4 hours, 24 hours, and 3-4 weeks post cTACE. Data will be collected and recorded on the Doxorubicin PK Worksheet.

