#### Instructions for processing PK samples:

Blood samples will be collected in a heparinized tube (6 mL) from subjects at the time points on the study collection calendars (baseline, 5, 10, 20, 40 min, 1, 2, 4, 24 hours, 3-4 weeks). Blood samples will be centrifuged at 1000x g (or 3000 rpm) for 10 minutes at 4°C and stored frozen at -20°C or below until analyzed. The samples will be analyzed for total plasma doxorubicin and doxorubicinol at the Analytical Pharmacology Laboratory at the Sidney Kimmel Comprehensive Cancer Center at Johns Hopkins.

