### Day 21-28

Standard of care clinical followup, H&P, labwork, MRI or CT imaging.  
PK blood draw at 3-4 weeks.

Please see appendices for additional study calendar.

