## 7. Statistical Methods

### 7.1 Primary Outcome Variable

Pharmacokinetic profile of doxorubicin and doxorubicinol after cTACE for each patient:

- Parameters of PK analysis including peak of the plasma concentration ( $C_{max}$ ), time of maximum concentration, and area under the concentration time-curve (AUC).
- PK profiles for each patient will be correlated with toxicity and tumor burden (size of target lesion), BSA and gender.
- Comparison of PK profile between lobar administration and superselective administration.

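### Does the missing AUC interval, with no draw between 24 hours and week 3-4, leave the primary PK comparison undefined?

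*Combined protocol and SAP*

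**What the plan says.** Section 7.1 lists among the primary parameters "area under the concentration time-curve (AUC", alongside the peak concentration and its time. Sections 2.1 and 7.1 also make the lobar/superselective comparison and the correlations part of the primary outcome. Section 7.3 gives the method as "Pharmacokinetic parameters will be calculated by standard noncompartmental methods using Phoenix WinNonlin 6.1", then a Mann-Whitney test between arms at P < 0.05.

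Section 5.1.2 puts the post-procedure samples at "5 minutes, 10 minutes, 20 minutes, 40 minutes, 1 hour, 2 hours, 4 hours, 24 hours, and 3-4 weeks post cTACE"; with baseline that makes ten. The last is tied to the routine follow-up visit (Section 5.2, Day 21-28: "PK blood draw at 3-4 weeks"). Of the assay, the sample-processing instructions say "The samples will be analyzed for total plasma doxorubicin and doxorubicinol", with no quantification limit.

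On incomplete sampling, Section 7.3 allows up to 40 consents for 30 patients "to account for patients who are unable to complete sample collection for the PK (80% of planned draws". Section 4.2 says that consented patients will "be assigned a study identifier and counted for the final data analysis", while Section 7.2 takes technical failures out of the study and Section 2.1 plans pharmacokinetics on all 30 patients. After the 16th patient, "the PK parameters will be measured for each patient in order to formally review the accumulated data", with protocol modification possible.

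**The concern.** AUC to a fixed time, to the last quantifiable sample and to infinity are different quantities, and the plan does not pick one. The schedule makes the choice look important. A single draw separates hour 4 from week 3, so a terminal slope has little support, and what is done with the late sample decides whether AUC ends at one day or at three to four weeks. The sample size rests on a 50% change in exposure, for which AUC is the natural measure. If two intervals gave different arm ratios from the same data, the interval could be chosen after the 16-patient review.

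The 80% figure adds to this. It sets no analysis rule, and a patient can meet it without the 24-hour sample. Section 4.2, taken literally, would put screen-outs and technical failures into the final analysis.

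**Working it through.** **1. The plan's own figures.** Section 7.3 states 8, 15 and 58 for CVs of 30%, 43% and 90%. Two one-sided t tests with margin 0.5, SD = CV, α = 0.05 and β/2 = 0.10 need n ≥ 2[(t₀.₉₅ + t₀.₉₀) × CV / 0.5]² per arm on 2n − 2 degrees of freedom. This gives 8, 14 and 57, within one of each stated value. The calculation uses a CV and a 50% change and no AUC interval, so the point leaves it untouched.

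**2. The gap.** Day 21 is 504 h: (504 − 24)/504 = 95.2%. Day 28 is 672 h: (672 − 24)/672 = 96.4%. This is a share of time, not of AUC.

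**3. The ordinary reading.** If the week 3-4 sample is unquantifiable, AUC to the last quantifiable sample stops at 24 h. Every fully sampled patient then has AUC0-24h, one common interval.

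**4. Does the interval change the comparison?** The documents give no concentrations, so the curves are assumed: C(t) = A·2^(−t/5 min) + B·2^(−t/1 h) + D·2^(−t/T), with zero at time 0, the planned draw times and linear-up/log-down trapezoids. AUC to infinity is AUC0-24h + C24/λ, with λ from the 2, 4 and 24 h draws. True total exposure is (A/12 + B + D·T)/ln 2. The superselective arm has A and B halved and D unchanged. Example, (90, 9, 1) with T = 24 h: true ratio = (3.75 + 4.5 + 24)/(7.5 + 9 + 24) = 32.25/40.5 = 0.796.

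| A, B, D | T (h) | Ratio, AUC0-24h | Ratio, AUC to infinity | True ratio |
|---|---|---|---|---|
| 90, 9, 1 | 12 | 0.681 | 0.714 | 0.711 |
| 90, 9, 1 | 24 | 0.712 | 0.796 | 0.796 |
| 90, 9, 1 | 48 | 0.730 | 0.875 | 0.872 |
| 85, 12, 3 | 12 | 0.790 | 0.832 | 0.827 |
| 85, 12, 3 | 24 | 0.820 | 0.929 | 0.895 |
| 85, 12, 3 | 48 | 0.836 | 1.035 | 0.941 |
| 70, 20, 10 | 12 | 0.879 | 0.916 | 0.911 |
| 70, 20, 10 | 24 | 0.900 | 0.997 | 0.951 |
| 70, 20, 10 | 48 | 0.911 | 1.100 | 0.974 |

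- AUC0-24h overstates the arm difference in all nine rows.
- AUC to infinity is nearer the truth in eight of nine, although within one arm it recovers only 0.61-0.98 of true exposure. Much of that shortfall cancels in the ratio.
- The two ratios above 1 occur where the true ratios are 0.941 and 0.974, differences of 6% and 3%.
- No entry reaches a 50% change.
- If A, B and D are all halved, every interval gives 0.5.

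**5. The 80% figure.** 0.8 × 10 = 8 draws, so a patient without the 24-hour and week 3-4 samples still qualifies, with the last concentration at 4 h. On these curves AUC0-4h is 0.29-0.64 of AUC0-24h, so the two should not be ranked together.

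**6. Who is analysed.** Consenting up to 40 to obtain 30, with incomplete samplers among the reasons, implies replacement. Section 2.1's 30 patients fits that, and Sections 5.5 and 7.2 deal with technical failure. Only the registration sentence in Section 4.2 stands apart, and patients who never received doxorubicin have no profile to analyse.

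**The case for a change.** The strongest case is that naming a method and a software package does not define an estimand, that tests at P < 0.05 are attached to it, and that one or two sentences would settle it at no cost. A Mann-Whitney test could fall on different sides of 0.05 under two intervals even when neither ratio approaches 50%. Substituting zero for the late sample with linear trapezoids would add 0.5 × 480 × C24 = 240·C24 at Day 21 and 0.5 × 648 × C24 = 324·C24 at Day 28, an artefact of visit timing. The 4-hour truncation follows from the text without any model.

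Part of this stands. The interval is unstated, and patients whose last usable sample is at 4 h need separate handling. The rest is weaker. No section proposes carrying AUC to a substituted zero. Nothing shows that missed 24-hour draws would differ between arms, and that draw falls on the same day as the routine CT. Halving only the early phases has no source in the documents. Section 5.1.1 says the amount given is titrated to the area treated; if exposure falls because less drug is given, and kinetics are proportional (an assumption), the whole curve scales and the interval is immaterial. Choosing the interval after the 16-patient review is possible, but nothing in the plan points to it.

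**Conclusion.** The observation is correct and no change follows. What is missing is analytic detail that a pharmacokinetic analyst fills in the ordinary way: AUC to the last quantifiable sample, which is AUC0-24h for complete profiles, with patients lacking the 24-hour sample contributing only the parameters their draws support. Section 4.2 is most plausibly a wording slip.

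No stated rule gives a wrong result, and prescribing an interval would be a trade-off. AUC0-24h rests on observed samples but overstates an early-phase difference in all nine curves; AUC to infinity tracks the ratio better in eight of nine but leans on a slope with one draw after 4 hours. The largest gap between the two ratios is 0.20 (0.836 against 1.035), where the true difference is 6%, against a planning change of 50%. The synopsis describes the study as not driven by a hypothesis, and Section 7.3 plans descriptive summaries beside the tests, which lowers the stakes further.

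This rests on the assumed curves (terminal half-life 12-48 h) and on the late sample being unquantifiable. On those curves the Day 21 concentration is at most 0.1% of the 24-hour value.
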